5.8. Concomitant Medication

Subjects should be treated with standard of care medications for HFpEF or associated comorbidities. As per inclusion criteria, subjects should be on a stable medical regimen for HFpEF prior to entry. Further adjustment of diuretics or blood pressure medications during the study period is discouraged and should only be performed according to new and clinically compelling worsening of clinical status. Therapy with organic nitrates or phosphodiesterase-5 inhibitors is contra-indicated during the study period.

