3.1. The nitrate–nitrite–NO activation pathway

NO formation occurs via 2 pathways in mammals (Figure 1): (1) NO synthases (NOS) catalyze the formation of NO from L-arginine and O_2 ;²⁸ (2) Circulating nitrate (previously considered an inert product of NO metabolism) can be converted to NO through the nitrate-nitrite-NO pathway, which is independent of NOS.²⁸⁻³³

The nitrate-nitrite-NO pathway is dependent primarily on dietary inorganic nitrate intake. Vegetables (leafy green vegetables and beetroot, in particular)^{28, 33-36} are the main source of inorganic nitrate in the diet (>80%). Oral cavity commensal bacteria reduce nitrate to nitrite, which has a high oral bioavailability(>90%).^{33, 35, 36} Nitrite present in the blood stream is reduced directly to NO, a reaction catalyzed by several molecules, particularly deoxygenated myoglobin,³⁷⁻⁴⁰ and deoxygenated hemoglobin,⁴¹ but also xanthine oxidoreductase,⁴² mitochondrial respiratory chain enzymes⁴³, aldehyde oxidase⁴⁴, carbonic anhydrase,⁴⁵ vitamin C⁴⁶, polyphenols^{47, 48} and even endothelial NO synthase.^{49, 50} Nitrate is also directly absorbed in the gastrointestinal tract (without requiring conversion to nitrite), with high bioavailability (>90%)⁵¹ and circulates in plasma with a half-life of ~6-8 hours, in contrast to nitrite, which has a very short half-life (~30-40 minutes).⁵²⁻⁵⁴ Circulating nitrate is taken up by the salivary glands and secreted in the saliva (thus being susceptible to both direct reabsorption as nitrate or to conversion to nitrite followed by absorption). This entero-salivary cycle provides a natural, "slow" and sustained source of nitrite from ingested nitrate, thus allowing for favorable pharmacokinetics and for safe oral administration of "pharmacologic" doses in HFpEF (as discussed further in this application). Most (65%) inorganic nitrate eventually undergoes renal excretion.

NO production by the nitrate-nitrite-NO pathway is enhanced under hypoxic conditions: exercising muscle is characterized by a low pO_{2} ,³³ which favors the formation of NO from circulating nitrite.

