- 13. Clinically significant lung disease as defined by: Chronic Obstructive Pulmonary Disease meeting Stage III or greater GOLD criteria, treatment with oral steroids within the past 6 months for an exacerbation of obstructive lung disease, or the use of daytime supplemental oxygen
- 14. Ischemia on stress testing without either (1) subsequent revascularization, or; (2) a subsequent angiogram demonstrating the absence of clinically significant epicardial coronary artery disease, as per investigator judgement.
- 15. Left ventricular ejection fraction <45% in any prior echocardiogram or cardiac MRI, unless this was in the setting of uncontrolled atrial fibrillation.
- 16. Treatment with phosphodiesterase inhibitors that cannot be withheld
- 17. Treatment with organic nitrates
- 18. Significant liver disease impacting synthetic function or volume control (ALT/AST > 3x ULN, Albumin <3.0 g/dL)
- 19. eGFR < 30 mL/min/1.73m²
- 20. G6PD deficiency. In males of African, Asian or Mediterranean decent, this will be formally evaluated by enzyme testing prior to drug administration. A negative screening test for G6PD will be required in these subjects for inclusion in the study. If a quantitative test is being performed, a clinically significant reduction in G6PD activity (<60% of normal) will exclude subjects.
- 21. Methemoglobinemia baseline methemoglobin level >5%
- 22. Serum K>5.0 mEq/L
- 23. Severe right ventricular dysfunction
- 24. Any medical condition that, in the opinion of the investigator, will interfere with the safe completion of the study.
- 25. Contraindications to MRI (except as noted below), including the presence of a pacemaker, metal implants, claustrophobia, or that have known medical conditions which can be exacerbated by stress such as anxiety or panic attacks. Inability to lie flat in the MRI scanner for 90 minutes is also an exclusion criterion.

Participants who have contraindications for MRI but are otherwise good candidates for the study, may be enrolled. In this case, participants will undergo all study procedures except for the MRI scans.** (See paragraph below for more detail)

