5.1. Initial Visit

During the baseline study visit, inclusion and exclusion criteria will be reviewed to ensure subject suitability. After subject eligibility is confirmed, written informed consent will be obtained from the subject using Institutional Review Board (IRB)-approved documents. Informed consent will be obtained before any study procedures. Subjects will be given the opportunity to have all questions regarding their participation answered in detail in a private setting before entering the study. Informed consent may be obtained in-person or virtually.

Following informed consent, a physical examination, with measurement of orthostatic blood pressures, will be performed. A urine pregnancy test will be performed in women with childbearing

potential. Blood will be collected for measurement of (a) comprehensive metabolic panel; (b) complete blood count; (c) NT-pro-BNP; and (d) methemoglobin. A pregnancy test (women of childbearing potential) and Glucose-6-phosphate dehydrogenase (G6PD) deficiency screening (males of males of African, Asian or Mediterranean decent) will be performed as needed. Blood, urine, and saliva samples will be collected and frozen for nitrate/nitrite level determination. Following the collection of baseline labs and biomarker samples, subjects will be provided with a standard low nitrate breakfast. The Kansas City Cardiomyopathy Questionnaire (KCCQ) will be administered. Subjects will also be given an informational brochure regarding foods that are high in nitrate/nitrite and will be instructed to avoid such foods while participating in the study.

Computerized cognitive assessment testing will be performed using cogstate software (Cogstate: New Haven, CT). The assessment includes a customized battery of seven tests that measure various cognitive domains. The battery includes the following tests:

- International Shopping List Test
- Gorton Maze Learning Test
- Detection Test
- Identification Test
- One Card Learning Test
- One Back Test
- International Shopping List Test- Delayed Recall (memory)

The system works with an internet server administered and maintained by Cogstate, which quantifies the subject's performance/responses and calculates cognitive scores. No personal identifiable information will be entered/uploaded into the server.

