We will document an intervention-related change in blood nitrate and nitrite. Nitrate and nitrite levels will be sampled before and approximately 2 hours after the last oral dose on the morning of the exercise test, after the patient has been on each intervention for approximately 6 weeks. Measurements will be performed at [name] lab at the University of Pennsylvania. Venous blood samples will be drawn into lithium-heparin tubes (which have very low levels of nitrate/nitrite) and centrifuged at 4,000 rpm for 10 min within 3 min of collection and frozen at - 80°C for later analysis. Blood will also be obtained at peak exercise. After thawing at room temperature, blood samples will be deproteinized using cold ethanol precipitation as previously described.¹¹⁸ The nitrate and nitrite content of deproteinized blood will be determined using a modified detection chemiluminescence technique using a lonics/Sievers nitric oxide analyzer (NOA 280), as first described by [name] lab¹⁴⁰ and later adapted by Allen et al for human blood.¹⁴¹

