Impact of NO₃⁻ on methemoglobin levels: Nitrate supplementation increases serum nitrite levels through the actions of an enterosalivary circuit and reduction of nitrate to nitrite by anaerobic bacteria in the oral cavity. ^{28, 33-36} Methemoglobin is generated by the reaction of nitrite with hemoglobin. According to Toxnet, doses between 2-9 grams of NO_3^- have been associated with methemoglobinemia. The dose we will use in our study (18 mmol KNO₃) will provide only 1.11 grams (18 mmol $NO_3^- x$ 62 grams/mol $NO_3^- x$ 1mol/1000 mmol), which is well below this threshold. Moreover, this level of nitrate supplementation provides less inorganic nitrate than that found in a traditional Japanese diet, which is rich in vegetables (traditional Japanese diet provides 18.8 mg/kg of nitrate per day x 70 kg individual = 1.3 grams of nitrate).¹⁷⁹ Moreover, not a single cases of methemoglobinemia was observed in our pharmacokinetics trial, at the same doses used in this trial and in the same patient population. In the pharmacokinetics study we measured methemoglobin every half hour after the first administration as well as during steady-state continued oral administration at doses of both 12 mmol/d and 18 mmol/d (same dosing scheme used in the KNO₃CK OUT HFpEFp trial) and did not find any clinically-significant elevations in methemoglobin. We don't anticipate any significant issues with methemoglobinemia in the KNO₃CK OUT HFpEFp study since this is a problem that has been reported with nitrite, but not with nitrate at the doses used in this study.

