Pilot safety data: In our double-blind randomized controlled trial in HFPEF, in which 12.9 mmol of inorganic nitrate were administered to patients with HFpEF, efficacy was demonstrated for the study endpoint (please refer to research plan). In this pilot study, **no side effects were noted in any subject**, except for pink urine (which was not different between the nitrate-rich and nitrate-poor beetroot juice, because this is a consequence of other components of beetroot juice). As the body is able to reduce oxidized Fe³⁺ in methemoglobin back to Fe²⁺ at a rate of approximately 15% per hour,¹⁸⁰ the gradual increase in nitrite that occurs after nitrate administration (and the consequent formation of methemoglobin), should occur slowly enough to prevent significant rises in methemoglobin. To the best of our knowledge, methemoglobinemia has not been reported with oral nitrate administration. In our pharmacokinetic study, we did not observe any clinically-relevant elevations in methemoglobin levels.¹⁷⁸

Other potential safety considerations: There has been concern regarding whether a high nitrate diet may predispose to gastric cancer in humans through conversion to nitrite in the stomach or through increased urinary excretion of nitrate metabolites. This is a controversial issue derived from animal studies¹⁸¹, although the relationship between nitrate intake and cancer has not been demonstrated in humans.^{31, 106, 182} In fact, many studies show either no relationship or even an inverse relationship between a high intake of nitrate and the occurrence of gastric cancer.^{183, 184185, 186} The Joint FAO/WHO Expert Committee on Food reviewed all the available evidence, but failed to establish a definite link between nitrate intake and risk of developing cancer.^{189, 190} Furthermore, The World Cancer Research Fund/American Institute of Cancer Research found no evidence linking ingestion of vegetables which are known to be high in nitrate with the development of cancer.¹⁹¹ We note that the highly controversial concern regarding cancer risk associated with nitrate intake is related to long-term intake and not a significant issue with our 6-week administration scheme of potassium nitrate.

11.2.2. Potential Risks of study procedures:

Potential risks are associated with the study tests, the study interventions (potassium nitrate) and potential breaches in confidentiality.

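### Antibacterial mouthwash is neither restricted nor specifically recorded, although the protocol names oral bacteria as the step that converts nitrate to nitrite

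*Combined protocol and SAP*

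**What the plan says.** **Activation.** Section 3.1 gives the route from nitrate to nitrite: "Oral cavity commensal bacteria reduce nitrate to nitrite". It adds that absorbed nitrate is taken up by the salivary glands and secreted into saliva, where it can be converted, and it describes this cycle as a slow, sustained source of nitrite. Section 11.2.1 again attributes the rise in serum nitrite to the enterosalivary circuit and to "reduction of nitrate to nitrite by anaerobic bacteria in the oral cavity". Section 4.4 gives the nitrate in a gelatin capsule.

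**What is controlled.**
- Diet: section 5.1 provides a brochure on foods high in nitrate or nitrite, and subjects "will be instructed to avoid such foods while participating in the study". Sections 5.3 and 5.5 repeat the message at each 1-week call and each 6-week visit.
- Drugs: section 4.3.2 excludes organic nitrates and "Treatment with phosphodiesterase inhibitors that cannot be withheld". Section 5.8 adds: "Therapy with organic nitrates or phosphodiesterase-5 inhibitors is contra-indicated during the study period".

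**What is not mentioned.** Mouthwash, oral antiseptics and antibiotics do not appear in the 25 exclusion criteria, the 6-week discontinuation criteria (4.3.3), section 5.8, the dietary instructions or the schedule of events. Sections 10.2 and 10.3 contain no covariate, subgroup or sensitivity analysis for such exposure.

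**What is measured.** Concomitant medications are recorded at both 6-week visits. Section 8.7 says "We will document an intervention-related change in blood nitrate and nitrite", with samples before and about 2 hours after the morning dose, and blood also at peak exercise. The synopsis lists an exploratory objective relating achieved nitrate and nitrite levels to response.

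**The concern.** The plan manages how much nitrate a subject takes in and which drugs might interact with it, but not the step that, on its own account, makes the capsule active. A swallowed capsule passes the mouth without contact, so on the protocol's description its nitrate meets oral bacteria only through saliva.

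Followed exactly, the plan permits antibacterial mouthwash up to the morning of the endpoint visit. Each phase has one maximal exercise test, and section 3.1 puts the half-life of nitrite at roughly 30 to 40 minutes, so nitrite at the test depends on recent conversion. A pill count would still show full adherence.

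The expected direction is one-sided. Less activation in the KNO3 phase weakens the effect, and on this pathway mouthwash use in the KCl phase does not offset that. At stake is an average effect shrunk toward zero on the co-primary endpoints and on the mechanistic endpoints that depend on nitrite.

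**Working it through.** **Inputs from section 10.1.** Effect 0.6 mL/kg/min in peak VO2; SD of the change 1.23; 84 enrolled; 90% retention; two-sided alpha 0.05; stated power 80%. Completers: 84 × 0.90 = 75.6, taken as 75.

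**Inputs not in the documents (assumptions).** The share of subjects exposed in the KNO3 phase, f, taken as 10%, 20% and 30%. The loss of activation in an exposed subject, taken as 100%, the worst case.

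**Step 1: the plan's own figure.** Power from the noncentral t for a paired difference, 73 df.
- Literal reading, with 1.23 as the SD of the paired change: 0.6 / 1.23 = 0.488; 0.488 × √75 = 4.22; power 98.6%.
- Alternative reading, with 1.23 as a within-period SD: SD of the difference = 1.23 × √2 = 1.739; 0.6 / 1.739 = 0.345; 0.345 × √75 = 2.99; power 83.8%.

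Neither gives 80% at 75 completers. The alternative reading gives 80.0% at 68 completers, which is 90% of the 76 subjects in Appendix 2. That mismatch is a separate matter; here it means only that both readings must be carried forward. The pilot result favours the literal one. Its percentages (88% male, 82% African-American) fit n = 17, which is inferred. A difference of 12.6 − 11.6 = 1.0 with SD 1.23 then gives t = 1.0 / (1.23 / √17) = 3.35 and P of about 0.004, close to the reported 0.005.

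**Step 2: dilution.** If a share f has zero effect and the rest have 0.6:
- mean = (1 − f) × 0.6
- variance = SD² + f(1 − f) × 0.6²

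Example, f = 0.20, literal reading: mean = 0.48; variance = 1.5129 + 0.0576 = 1.5705; SD = 1.253; 0.48 / 1.253 × √75 = 3.32; power 90.5%.

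| f fully blocked | Average effect | Power, 1.23 = SD of paired change | Power, 1.23 = within-period SD |
|---|---|---|---|
| 0% | 0.60 | 98.6% | 83.8% |
| 10% | 0.54 | 96.0% | 75.1% |
| 20% | 0.48 | 90.5% | 64.7% |
| 30% | 0.42 | 81.3% | 53.1% |

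Power reaches 80% at f of about 31% on the literal reading and about 5% on the alternative. If each exposed subject loses only a fraction b of the effect, the average becomes 0.6 × (1 − f × b), so partial blocking makes every loss smaller.

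**The case against.** Several objections have force.

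1. **The link to mouthwash is not in the documents.** They name oral bacteria as a route but never mention mouthwash, say how far it would reduce conversion, or call the route the only one. Section 11.2.1, when describing the cancer-risk debate, also refers to nitrate acting "through conversion to nitrite in the stomach". A reader might infer that exposed subjects receive a drug that cannot be activated; the documents do not support that. This stands.
2. **Conversion is measured.** A reader might infer that a null result could not be told apart from failed activation. That is wrong. Blood nitrate and nitrite are assayed in each phase, and high nitrate with low nitrite is what poor conversion would look like. What remains is that the assays come after the event and do not identify the cause.
3. **Antibiotics are probably captured already,** through the concomitant-medication record. This stands, and it narrows the gap to mouthwash.
4. **An 80% starting point overstates the loss for peak VO2.** Starting from 80% gives Φ(2.80 × (1 − f) − 1.96), about 71%, 61% and 50% at the three values of f. Those figures do not apply to peak VO2, whose stated inputs give 98.6% on the literal reading.
5. **An instruction may exist elsewhere.** The dietary brochure and the Manual of Procedures are not in the package, so the point concerns what the protocol itself requires.
6. **Usual oral hygiene may be the intended setting.** The trial seeks a representative sample and a readily implementable therapy. This is a fair choice of question, but the protocol does not state it, and without a record of use the result could not be described in those terms.

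**Conclusion.** The omission is real: the protocol names the bacterial step and leaves the most obvious everyday threat to it unrestricted and unrecorded. The likely bias is toward no difference, and it arises from exposure in the KNO3 phase. That mouthwash reduces conversion is an inference from the protocol's mechanism, not something it states.

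The size is unknown. The figures of 0.54, 0.48 and 0.42 mL/kg/min, and the powers beside them, rest on assumed exposure of 10% to 30% with complete blocking. On the better-supported reading of the SD, peak VO2 keeps at least 80% power until nearly a third of subjects are wholly blocked. On the other reading, about 5% is enough. The documents therefore support neither a claim that the trial is underpowered for this reason nor a claim that KNO3 is inert in exposed subjects. This is an inexpensive improvement to the design, not a flaw that undermines it.

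**What to change.** - **Instruction.** Add to section 5.8, the dietary brochure and the existing counselling (baseline, both 1-week calls, both 6-week visits) a request to avoid antibacterial mouthwash during both treatment phases, including on the morning of the endpoint visit. Use the same words in each phase, so that the blind and the within-subject comparison are unaffected.
- **Record.** Add one case-report-form question per phase on mouthwash use and when it was last used. Flag antibiotic use from the concomitant-medication record already collected. No clinically needed treatment changes.
- **Analysis.** Keep the intention-to-treat analysis primary. Label any analysis by exposure or by achieved nitrite as a sensitivity analysis. Dropping exposed periods selects on a post-randomisation event and, in an AB/BA design, removes that subject's paired contrast. Antibiotic use may also mark an illness that itself lowers exercise capacity.

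The cost is one line in existing materials, one form question and a slight burden on subjects. The result would then apply to people who do not use such mouthwash, and the report should say so.

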6. DRUG DISPENSING, ACCOUNTABILITY, AND DESTRUCTION

Drug dispensing will be managed by the Penn Investigational Drug Pharmacy, in collaboration with the Northwestern Investigational Drug Pharmacy. KNO₃ and KCI capsules will be compounded at the Penn IDS. Penn IDS will bottle, label, and dispense product for the Penn and VA sites. Penn IDS will ship product to Northwestern IDS for bottling, labeling, and dispensing of product at the Northwestern site. Prior to initiation of each phase, participants will receive a sufficient supply of KNO₃ or placebo capsules to last until the end of each treatment phase, allowing for 100% compliance with the regimen for the entire treatment phase, including a window of \pm 7 days for the 1-week up-titration (to ensure an adequate supply of medication) and \pm 1 week for the 6-week endpoint assessment visit.

Subjects will be instructed to take the medication as required by the protocol, and compliance will be assessed via pill count performed by IDS.

Subjects will be instructed to return unused capsules at the end of each treatment phase. A pill count will be performed prior to destruction of the drug. Returned trial capsules will be stored separately from the non-allocated trial capsules until returned trial capsules are disposed of. The IDS personnel will keep track of all received, used, partly used and unused trial products.

Used and unused study drug will be destroyed at the instruction of the sponsor. A copy of the drug destruction SOP should be maintained in the pharmacy section of the Regulatory Binder. Study drug should not be destroyed until drug accountability has been completed and the Sponsor has authorized it.

6.1. Rules for un-blinding

Randomization data will be kept strictly confidential, accessible only to authorized IDS personnel, until the time of un-blinding. The investigators will be given access to the treatment code for their patients for emergency un-blinding by calling the respective IDS. This is considered to be a very unlikely occurrence. Any suspected study drug-related events will be treated as though the patient received active (KNO₃). Nevertheless, in the rare event of emergency un-blinding, the site PI and the Sponsor must be notified.

7. ADVERSE EVENTS

7.1. Key definitions

Adverse Event: An adverse event (AE) is any untoward medical occurrence associated with the use of a drug in a subject whether or not considered drug or biologic related. An AE can therefore be any unfavorable and unintended sign, symptom, or disease temporally associated with the use of the pharmaceutical product.

Suspected Adverse Reaction: A suspected adverse reaction (SAR) is any adverse event for which there is a reasonable possibility that the drug caused the event. "Reasonable possibility" suggests there is a causal relationship between the drug and the adverse event. "Suspected adverse reaction" implies a lesser degree of certainty about causality than adverse reaction, which means any adverse event caused by a drug.

Serious Adverse Events (SAE): An adverse event or suspected adverse reaction is considered serious if the investigator or sponsor believes any of the following outcomes may occur:

- Death
- Life-threatening AE: Places the subject at immediate risk of death at the time of the event as it occurred. It does not include an AE that, had it occurred in a more severe form, might have caused death.
- Persistent or significant incapacity or substantial disruption of the ability to conduct normal life functions.
- Inpatient hospitalization or prolongation of hospitalization.
- Congenital anomaly or birth defect.
- Important medical events that may not result in death, be life threatening, or require hospitalization may be considered a serious adverse event when, based upon appropriate medical judgment, they may jeopardize the subject and may require medical or surgical intervention to prevent one of the outcomes listed in this definition above.

This determination is based on the opinion of either the investigator, or sponsor (i.e., if any one of these believes it is serious, it must be considered serious).

Unanticipated Adverse Device Effect (ADE): Any serious adverse effect on health or safety, any life-threatening problem or death caused by, or associated with a device, if that effect, problem, or death was not previously identified in nature, severity, or degree of incidence in the application; or any other unanticipated serious problem associated with a device that relates to the rights, safety, or welfare of subjects.

